7.4 Treatment Procedures

The treatment session lasts approximately 20 minutes and may be performed in an office environment. Treatment is applied in the physician's office. For session and treatment details (see below)

During the treatment, the same total number of shocks will be delivered according to the two treatment schedules as follows:

Group A:

5 daily sessions within a week (MTWThF), in which 720 shocks of treatment energy will be applied in every session to each treated region (left and right corpora cavernosa and crura).

Group B:

Three sessions per week (MWF) for 2 consecutive weeks, in which 600 shocks of treatment energy will be applied in every session to each treated region (left and right corpora cavernosa and crura)

Following the last treatment session, each patient will resume his baseline consumption of PDE5i, in terms of type and dose of drug, for the remainder of study duration.

7.5 Follow-Up Procedures and Evaluations:

Follow-up visits will be conducted at month 1, month 3 and month 6 after the last treatment session and shall include:

Measuring IIEF-EF, GAQ, SEP, and EHS scores of patients at the clinic at every follow-up visit

Reporting and recording adverse events at every follow-up visit.

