2. HYPOTHESIS

2.1 Alternate Hypothesis (H_A):

Active Treatment groups will show a >2-point increase in the IIEF-EF score from baseline for mild erectile dysfunction, and >5 points for moderate erectile dysfunction and will show significant change.

2.2 Null Hypothesis (H₀):

There is no difference from baseline and after-treatment in Treatment groups for alleviating ED measured using IIEF-EF score.

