3. OBJECTIVES

3.1 Primary Efficacy Objective

To evaluate change of IIEF-EF score⁹ from baseline to follow-ups 1, 3 and 6 months' post treatment (appendix I).

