4.2 Duration of Study Participation

The total duration of the study will be for 7 months— including 1-month pretreatment (washout) followed by a period of 6 months' follow-up after the treatment.

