7.3 Pre-Treatment Procedures and Evaluations

Upon evaluating the inclusion/exclusion criteria, patients will be recruited to the study and randomized into one of the two groups in a 1:1 ratio (randomization will be performed by a computer software maintained by the Department of Urology). Patients randomized to the treatment groups will be instructed to stop any use of PDE5i for 4 weeks prior to first treatment session and refrain from using any other ED therapy option during the study. They will be instructed to undergo a PDE5i washout period of 4 weeks prior to treatment and to avoid using PDE5i or any other ED treatment during the entire study duration (shockwave treatment and follow-ups). After the washout period and before the first treatment session, patients will answer the IIEF-EF, SEP and EHS questionnaires for baseline evaluation.

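### Sections 7.3 and 7.4 give opposite PDE5i rules for follow-up; with the post-washout baseline, resuming the drug makes prior users' IIEF-EF change an on-drug minus off-drug difference

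*Combined protocol and SAP*

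**What the plan says.** Three statements in section 7.3 matter. Men are "instructed to stop any use of PDE5i for 4 weeks prior to first treatment session and refrain from using any other ED therapy option"; taken alone, this is a washout rule and is compatible with restarting PDE5i later. The next sentence goes further and tells them "to avoid using PDE5i or any other ED treatment during the entire study duration (shockwave treatment and follow-ups". The section then fixes the timing of baseline: "After the washout period and before the first treatment session, patients will answer the IIEF-EF, SEP and EHS questionnaires for baseline evaluation".

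Section 7.4 gives the opposite rule for the period after treatment: "Following the last treatment session, each patient will resume his baseline consumption of PDE5i, in terms of type and dose of drug". It applies to the end of the study, so it covers every follow-up visit listed in section 7.5.

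The primary objective (section 3.1) is the IIEF-EF change "from baseline to follow-ups 1, 3 and 6" months after treatment. Section 2 expects a ">2-point increase in the IIEF-EF score from baseline for mild erectile dysfunction, and >5 points for moderate erectile dysfunction", against the null that "There is no difference from baseline and after-treatment in Treatment groups for alleviating ED measured using IIEF-EF score". Section 10.5 names one IIEF-EF analysis, a repeated-measures ANOVA comparing the trends of groups A and B, and does not mention PDE5i.

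Section 7.2 records drug type and dosage for men who used PDE5i in the four weeks before screening. The follow-up items in section 7.5 do not include PDE5i use. The calendar in section 17, as far as it can be read, marks the questionnaires at screening and not at the pre-treatment visit.

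**The concern.** For a prior user the two rules are incompatible throughout the period in which the primary endpoint is measured. Site staff must choose, and different staff or patients may choose differently. Prior users would then be assessed in different drug states, and because PDE5i use is not among the listed follow-up items, nothing ensures that the state can be reconstructed later.

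The conflict also affects what the primary endpoint means. Section 6.1 admits only men who respond to PDE5i at maximal dose, so restarting a usual dose could plausibly raise scores, although that dose may be below the maximum. If baseline is taken off drug and follow-up on drug, the null of no change from baseline could be rejected because a drug was restarted. Men who did not use PDE5i before the study are unaffected.

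**Working it through.** The plan gives no figure on this point, so there is none to reproduce.

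**Can the two rules be reconciled?** One could try reading the consumption to be resumed in 7.4 as use at the post-washout baseline. That use is nil, so there would be nothing to resume and no type or dose to specify. The phrase fits the pre-washout use recorded under 7.2. The second PDE5i sentence in 7.3 names follow-up explicitly. No reading satisfies both.

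**Drug state at each assessment, for a prior user.** The washout lasts 4 weeks and the IIEF-EF recall period (Appendix I) is also 4 weeks, so the 7.3 baseline describes an off-drug period. Under 7.4 the drug restarts after the last session, so the month 1, 3 and 6 recall periods are on drug.

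**Size of the shift.** Let p be the share of prior users and d the IIEF-EF points added by their usual dose. Code drug state as 1 (on) or 0 (off). The drug's contribution to the mean within-group change is

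p × (state at follow-up − state at baseline) × d.

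| PDE5i rule in follow-up | Baseline used | Contribution |
|---|---|---|
| Ban (7.3) | Post-washout (7.3) | p(0 − 0)d = 0 |
| Resume (7.4) | Post-washout (7.3) | p(1 − 0)d = +pd |
| Resume (7.4) | Screening | p(1 − 1)d = 0 if use was steady |
| Ban (7.3) | Screening | p(0 − 1)d = −pd |

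The last row arises only if the calendar, rather than the text of 7.3, is taken to set the baseline.

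The documents give neither p nor d. Over an assumed range, the shift +pd in points is:

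| p | d = 2 | d = 4 | d = 6 | d = 8 |
|---|---|---|---|---|
| 25% | 0.5 | 1.0 | 1.5 | 2.0 |
| 50% | 1.0 | 2.0 | 3.0 | 4.0 |
| 75% | 1.5 | 3.0 | 4.5 | 6.0 |
| 100% | 2.0 | 4.0 | 6.0 | 8.0 |

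The d at which the drug alone equals a section 2 threshold is threshold / p. For p = 25%, 50%, 75% and 100%:

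- mild, 2 points: 2/0.25 = 8; 2/0.5 = 4; 2/0.75 = 2.7; 2/1 = 2.
- moderate, 5 points: 5/0.25 = 20; 5/0.5 = 10; 5/0.75 = 6.7; 5/1 = 5.

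The thresholds are set by severity, so p and d should be read within each severity group. These are break-even values, not evidence of likely bias.

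**Effect on A versus B.** If both arms follow one rule, the contributions cancel in expectation under randomisation. What remains is chance imbalance in the share of users, multiplied by d. A 10-percentage-point imbalance gives 0.1 × 2 = 0.2 to 0.1 × 8 = 0.8 points.

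**The case against.** The strongest reply is that little inference is at risk. The only IIEF-EF analysis named is the comparison of A and B, which is unbiased in expectation under a single rule. With two active arms and no sham (section 7.1), the within-group change could not be credited to shockwaves even if the PDE5i text were consistent. Both statements are correct. But the protection of A versus B depends on one rule being applied in both arms, which contradictory text cannot ensure. The missing sham does not make the conflict moot either: restarting an active drug between baseline and follow-up adds a separate, avoidable cause of change.

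The text of 7.3 could also be taken to settle the matter, since its baseline fits the ban. Against that, the recording of type and dosage in 7.2 fits resumption. These cues point in different directions and do not show which sentence was meant to stand.

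The calendar is weak evidence on baseline timing. It was read by machine, a mark may have been lost, and the same row places GAQ at screening, before any treatment. The explicit sentence in 7.3 is therefore taken as governing. The flowchart in section 18 and a figure in section 7.2 could not be seen.

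A reader might infer that men who follow 7.4 would be withdrawn as non-compliant and lost. Section 5.3 does not support that: withdrawal is the investigator's decision, and randomised men stay in an intention-to-treat analysis whatever the reason.

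**Conclusion.** The contradiction is real and must be fixed: prior users are given opposite medication instructions for the whole primary-endpoint period. That conclusion rests on the text alone and not on an estimated bias.

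If 7.4 is followed with the 7.3 baseline, the mean within-group change shifts by p × d, for example 2 points at p = 50% and d = 4. This assumes that prior users resume their usual dose and that it raises their score by d on average. The actual size is unknown.

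Two stronger readings are tempting and are not supported. A reader might infer that the comparison of the two schedules is biased; under one uniformly applied rule it is not, in expectation. A reader might also infer that any improvement would be due to the drug, or that resolving the conflict would allow improvement to be credited to shockwaves. The documents give no p or d to support the former, and the absence of a sham arm rules out the latter.

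**What to change.** State one PDE5i rule and match the baseline to it. The documents do not settle the choice.

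- **(a) Keep the ban.** Delete the resumption sentence in 7.4 and keep the post-washout baseline. The cost is that prior users stay off an effective drug for about seven months (section 4.2: "including 1-month pretreatment (washout) followed by a period of 6" months of follow-up, so 1 + 6 = 7), with possible effects on recruitment and dropout.
- **(b) Allow resumption.** Delete the follow-up ban in 7.3 and use the pre-washout screening IIEF-EF as baseline for all men, users and non-users alike, including for classification as mild or moderate. A single baseline definition avoids mixing pre- and post-washout scores in one repeated-measures model. State in 7.2 that SEP and EHS are also taken at screening, since its text names only IIEF-EF, and record frequency of PDE5i use there as well as type and dose. The cost is reliance on steady use before screening, and some regression to the mean is possible because the screening score also decides eligibility.

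Under either option, make the calendar show the chosen baseline visit and record PDE5i use over the preceding 4 weeks at each follow-up. Report that use descriptively or in a sensitivity analysis, not as a simple covariate in the A-versus-B model, because it is measured after randomisation. Do not attribute the within-group change to shockwaves alone. The shared cost is amended wording, a calendar correction and one question per follow-up visit, with no extra patients or visits.

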7.2 Screening Evaluations and Procedures

The first visit of the patients will be for screening and medical evaluation. Patient's medical co-medication history will be collected and documented and a physical examination will be performed.

Previous month's blood test results will be reviewed including a general chemistry panel, a lipid profile, A1C and Testosterone levels during chart review.

Patients will sign an informed consent and will answer the IIEF-EF questionnaire to see if they fit the criteria for enrollment. In case they meet all inclusion criteria (and do not meet any exclusion criteria), they will be recruited to the study.

[figure not shown]
Patients who have been using PDE5-i in the last 4 weeks will report on their medicine type and dosage, and this data will be recorded in their files (reported prior to consent and gathered from chart review).

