11.8 Essential Documents for the conduct of a clinical trial

Essential documents are those documents with individually and collectively permit evaluation of the conduct of a trial and the quality of the data produced.

The following documents will be on file:

- CV’s and license of all investigators.
- IRB documentation/correspondence.
- Documentation of IRB certification.

12. Appendix I International Index of Erectile Function (IIEF – EF) Questionnaire.⁹

Name:	Date:
Write the number that best describes your erectile function for the past 4 weeks in the spaces provided	
Over the past four weeks: 1. How often were you able to get an erection during sexual activity?	0 = No sexual activity 1 = Almost never/never 2 = A few times (much less than half the

	
time) 3 = Sometimes (about half the time) 4 = Most times (much more than half the time) 5 = Almost always/always

2. When you had erections with sexual stimulation, how often were your erections hard enough for penetration?	
0 = No sexual activity 1 = Almost never/never 2 = A few times (much less than half the time) 3 = Sometimes (about half the time) 4 = Most times (much more than half the time) 5 = Almost always/always

3. When you attempted sexual intercourse, how often were you able to penetrate (enter) your partner?	
0 = Did not attempt intercourse 1 = Almost never/never 2 = A few times (much less than half the time) 3 = Sometimes (about half the time) 4 = Most times (much more than half the time) 5 = Almost always/always

4. During intercourse, how often were you able to maintain your erection after you had penetrated (entered) your partner?	
0 = Did not attempt intercourse 1 = Almost never/never 2 = A few times (much less than half the time) 3 = Sometimes (about half the time) 4 = Most times (much more than half the time) 5 = Almost always/always

5. During sexual intercourse, how difficult was it to maintain your erection to completion of intercourse?	
0 = Did not attempt intercourse 1 = Extremely difficult 2 = Very difficult 3 = Difficult 4 = Slightly difficult 5 = Not difficult

15. How would you rate your confidence that you could get and keep an erection?	
1 = Very low 2 = Low 3 = Moderate

	4 = High 5 = Very high
--	---------------------------

13. Appendix II Sexual Encounter Profile (SEP- Questions 2 and 3)¹⁰

SEP-Q2: Over the past 4 weeks, were you able to insert your penis into your partner's vagina?

Yes.....

No.....

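### Use of PDE5i and other ED treatment is specified as a data item only at screening, so washout adherence, use in each scoring window and differences in use between arms cannot be checked

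*Combined protocol and SAP*

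**What the plan says.** **Screening (7.2).** On other drugs: "Patient's medical co-medication history will be collected and documented". On the drug class that matters most here: "Patients who have been using PDE5-i in the last 4 weeks will report on their medicine type and dosage". The second record looks back over the four weeks before screening.

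**Post-washout baseline (7.3).** After a 4-week washout, "patients will answer the IIEF-EF, SEP and EHS questionnaires for baseline evaluation". The washout is an instruction to the patient; nothing is listed that records whether he followed it.

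**Follow-up at months 1, 3 and 6 (7.5).** The list has two items: "Measuring IIEF-EF, GAQ, SEP, and EHS scores of patients at the clinic at every follow-up visit", and adverse events.

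**Rule on PDE5i after treatment.** Section 7.3 tells patients to "avoid using PDE5i or any other ED treatment during the entire study duration". Section 7.4 says that after the last session "each patient will resume his baseline consumption of PDE5i, in terms of type and dose of drug, for the remainder of study duration". These two statements contradict each other.

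**Study calendar (section 17).** No row is named for PDE5i or concomitant treatment. A row called 'Record Treatment Parameters' is marked at the treatment visits and again at the three follow-up visits, and is not defined.

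**Analysis (10.5).** IIEF-EF and EHS go into a repeated-measures ANOVA; SEP, GAQ and success rates are compared by Fisher's exact test. There is no term or handling rule for ED drug use.

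**The concern.** Every efficacy endpoint (IIEF-EF, SEP2, SEP3, GAQ, EHS) measures what a PDE5i is taken to improve, and section 6.1 admits only men who respond to that class. The hypotheses in section 2 concern change from baseline within the treated groups, and 7.1 describes two active groups with no sham arm to absorb other causes of change.

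The instruments do not fill the gap. SEP2, for example, asks "Over the past 4 weeks, were you able to insert your penis into your partner's vagina", and a yes with a tablet looks the same as a yes without one. The GAQ asks about the treatment the patient has been taking without naming shockwave, so it could be answered about a tablet.

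The gap remains whichever way 7.3 and 7.4 are reconciled. If PDE5i is to be avoided, breaches are not seen. If it is to be resumed, the screening record shows the intended type and dose, not what was used in the four weeks that each questionnaire covers. Use that is not asked about at the visit cannot be reliably reconstructed afterwards.

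**Working it through.** **1. What is specified, visit by visit**

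| Visit | Outcome data | ED drug use specified? |
|---|---|---|
| Screening (7.2) | IIEF-EF for eligibility | Yes: PDE5i type and dose, co-medication history |
| Post-washout baseline (7.3) | IIEF-EF, SEP, EHS | No |
| Months 1, 3, 6 (7.5) | IIEF-EF, GAQ, SEP, EHS, adverse events | No |

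The one record of use precedes the washout, so it covers none of the windows that enter the analysis.

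**2. The plan's own figures.** The documents give no figure for drug effect or drug use. The nearest are the SEP2 rates in 10.5 (5% versus 35%). The power table built on them reproduces: the Walters approximation to Fisher's exact test at two-sided alpha 0.025 gives 0.813, 0.852 and 0.900 at 37, 40 and 45 per group, as printed. This point does not alter that table.

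**3. Direction and possible size on IIEF-EF (assumed values).** Let the drug add E points on average, let a share f of men use it in a follow-up window, and let a share w have used it in the baseline window despite the washout. Then

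shift in mean change from baseline = E × (f − w).

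- Follow-up use only (w = 0): a 2-point shift, the size of the mild-ED threshold in 2.1, needs f = 2/E. For E = 3, 5, 7 this is 0.67, 0.40, 0.29.
- Washout failure only (f = 0): the same shares give a shift of −2 points.
- Equal shares (f = w): no net shift.

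The 5-point threshold for moderate ED would need f = 5/E. This exceeds 1 for E = 3, equals 1.00 for E = 5 and is 0.71 for E = 7. A uniform gain is also impossible at the top of the entry range: a man who enters at 25 on a scale ending at 30 can gain at most 30 − 25 = 5.

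**4. Between arms (assumed values).** If use differs by d between arms, the A minus B difference moves by E × d. For d = 0.20 and E = 3, 5, 7 this is 0.6, 1.0, 1.4 points. The direction is open: if men who fail treatment are the ones who take a tablet, more use in the worse arm would hide a true difference.

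**5. SEP2 (assumed pass rate on drug).** With no shockwave effect, 5% passing off drug and users passing at rate u, the overall rate is 0.05 × (1 − f) + u × f. It reaches the planned 35% at f = (0.35 − 0.05)/(u − 0.05):

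- u = 0.80: 0.30/0.75 = 0.40
- u = 1.00: 0.30/0.95 = 0.32

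The data specified in the plan would not supply f, w or d.

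**The case against.** **The information may be captured anyway.** 'Record Treatment Parameters' is marked at months 1, 3 and 6, section 11.4 requires progress notes for each visit, and the CRFs and the section 18 flowchart were not available for this review. This stands to the extent that one cannot say the data will never exist. But none of the available text names ED treatment, and incidental notes are not a uniform record. The supportable statement is that the item is not specified.

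**A reader might infer that the randomised comparison is biased.** The documents do not support that. Section 5.3 provides for intention-to-treat analysis, and drug use after randomisation does not invalidate A versus B as a comparison of schedules. Nor do the documents give a reason to expect a particular imbalance in use. What is lost is the ability to examine it.

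**A reader might infer that recording use would isolate the shockwave effect.** It would not if PDE5i is resumed as in 7.4: baseline would be off drug, follow-up on drug, and there is no sham arm. Recording is necessary for attribution but not sufficient.

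**A reader might infer a definite inflation of 2 points or so.** The figures above are illustrations on assumed values. They leave the sign open, because washout failure acts against follow-up use.

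**Conclusion.** The gap is real and worth closing. Use of PDE5i or other ED-active treatment is specified at screening only. As written, the plan cannot show whether the washout was kept, how much drug was used in each scoring window, or whether use differed between arms, so within-arm change from baseline cannot be interpreted as a shockwave effect. A versus B stands as a comparison of schedules, though its explanation could not be probed.

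The size is unknown. On the assumed values, a shift comparable with the 2-point mild-ED threshold would need a net 29% to 67% of men using the drug, and the planned SEP2 rate could be reached without any shockwave effect at 32% to 40% use. These show that the matter is not negligible; they do not estimate what will happen. The conclusion rests on the data-collection lists, not on these numbers.

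**What to change.** 1. Reconcile 7.3 and 7.4 on PDE5i use after treatment. The later steps refer to whichever rule results.
2. Add to 7.3, 7.5 and the calendar one CRF item at the post-washout baseline and at months 1, 3 and 6: any PDE5i, other ED therapy, or new or changed drug affecting erection in the past four weeks, with type, dose, and number of attempts with and without it.
3. Define what 'Record Treatment Parameters' means at follow-up visits.
4. In 10.5, keep the intention-to-treat analysis as primary and tabulate use by arm and visit.
5. Prespecify a sensitivity analysis that keeps all patients. SEP2, SEP3 and GAQ yes answers from windows with use outside the reconciled rule count as non-response, and IIEF-EF in those windows is assigned no improvement from baseline. Simply dropping those IIEF-EF scores would be unsound: if men whose treatment fails are the likelier users, it would selectively remove failures and inflate the mean change.
6. State that recording is necessary but not sufficient for attributing change to shockwave if follow-up scores may be on drug.

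Cost: one short item at four existing visits, one table and one sensitivity analysis, with no extra visit, test or staff. The downside is that self-reported use is imperfect.

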1.4 Preliminary Studies

Contemporary literature shows two important studies in this field both conducted by Vardi et al^{7,8}.

The efficacy trial study published in 2010 recruited 20 men with vasculogenic ED and were given serial 2 sessions of treatment for about 3 weeks followed by 3 – week no intervention period. At 1-month duration there was a significant improvement in their erectile function measured by International Index of Erectile Function ED (IIEF-ED) domain scores (20.9 5.8 vs 13.5 4.1, $p < 0.001$). This significant result was consistent at 6-month follow up. Moreover, no pain or adverse event was noted during the follow-up period.

The second randomized, double-blind, sham controlled study by showed that treatment group showed better outcome than control group measured using International Index of Erectile Function-Erectile Function domain (mean SEM 6.7 0.9 vs 3.0 1.4, $p 0.0322$) at the first follow-up. Additionally, penile hemodynamics improve significantly in the treatment group in comparison to control group (maximal post-ischemic penile blood flow 8.2 vs 0.1 ml per minute per dl, $p 0.0001$).

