7. STUDY DESIGN, CLINICAL, RADIOLOGICAL, LABORATORY AND SURGICAL EVALUATIONS

7.1 Study Design

This is a prospective, randomized, clinical study aimed to evaluate the safety and efficacy of the two treatment schedules on symptomatic ED patients. The patients are randomized in a 1:1 ratio into two active treatment groups. (Refer section 18)

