10. STATISTICAL CONSIDERATIONS

10.1 Primary Study Endpoints

The IIEF-EF questionnaire (appendix I) was chosen as the primary clinical efficacy assessment tool in this study. The total score (range 0-30) will be used for statistical analysis.

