SEP-Q3: Over the past 4 weeks, did your erection last long enough for you to have successful intercourse?

Yes.....

No.....

14. Appendix III Global Assessment Question (GAQ)¹⁰

GAQ-Q1: Over the past 4 weeks, has the treatment you have been taking improved your erectile function?

Yes.....

No.....

GAQ-Q2: If yes, has the treatment improved your ability to engage in sexual activity over the past 4 weeks?

Yes.....

No.....

15. Appendix IV EHS- Erection Hardness Score.¹¹

How would you rate the hardness of your erection?

- 0: Penis does not enlarge
- 1: Penis is larger but not hard
- 2: Penis is hard but not hard enough for penetration
- 3: Penis is hard enough for penetration but not completely hard
- 4: Penis is completely hard and fully rigid

[figure not shown]
16. List of Abbreviations

ED	Erectile Dysfunction
AE	Adverse Event
EHS	Erection Hardness Score
GAQ	Global Assessment Questions
IIEF-EF	The International Index of Erectile Function – Erectile Function
LISW	Low Intensity Shock Wave
PDE5i	Phosphodiesterase type 5 inhibitor
SEP	Sexual Encounter Profile

17. Study Calendar

Visit #, Time Activity	Visit 1 Screening	Visit 2 Pre-Treatment	Week 1 Visits 3-7 5 Treatment	Week 1 Visits 3-5 3 Treatment	Week 2 Visits 6-8 3 Treatment sessions	Visit 8/9 1 Mo FU	Visit 9/10 3 Mo FU	Visit 10/11 6 Mo FU
Medical & Urological History	•							
Physical Examination	•							
Informed Consent	•							
Inclusion & Exclusion Criteria	•							
IIEF-EF, GAQ, SEP, EHS	•					•	•	•
Study Recruitment & Group Randomization		•						
Record Treatment Parameters			Group A	Group B	Group B	•	•	•
Report Complications			•	•	•	•	•	•

18. Study Design Flowchart:

19. References:

2. MELMAN A and GINGELL JC: THE EPIDEMIOLOGY AND PATHOPHYSIOLOGY OF ERECTILE DYSFUNCTION. *The Journal of Urology* 1999; **161**: 5–11.

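### All efficacy endpoints are self-reported by men who know their schedule, and no protection after allocation is stated: fix when forms are completed and code the arms for analysis (cheap, low priority)

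*Combined protocol and SAP*

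**What the plan says.** **Endpoints.** Section 10.1 states: "The IIEF-EF questionnaire (appendix I) was chosen as the primary clinical efficacy assessment tool in this study". The secondary endpoints are SEP questions 2 and 3, GAQ and EHS (3.2, 10.2). All are the man's own ratings. Appendix I tells him "Write the number that best describes your erectile function", Appendix IV asks "How would you rate the hardness of your erection", and Appendix III asks "has the treatment you have been taking improved your erectile function". Penile duplex ultrasound appears only as an eligibility test (6.1), so no objective efficacy measure is planned at follow-up.

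**Arms.** Section 7.1: "The patients are randomized in a 1:1 ratio into two active treatment groups". Section 7.4 gives group A five sessions in one week and group B six sessions over two weeks, with no sham visits.

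**Collection.** At baseline, after the washout, "patients will answer the IIEF-EF, SEP and EHS questionnaires for baseline evaluation" (7.3). At months 1, 3 and 6 the text is "Measuring IIEF-EF, GAQ, SEP, and EHS scores of patients at the clinic at every follow-up visit" (7.5). Who hands out, explains or collects the forms, and at what point in the visit, is not stated.

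**Masking.** The only related text is in 10.6: sealed envelopes, with the principal investigator and coordinator unaware of the group in advance. Section 10.5 describes the comparisons of A and B without mentioning coded arms. The independent surgeon monitor in section 9 covers data quality and safety, not outcome collection.

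**The concern.** Sealed envelopes protect assignment, and that protection ends when the envelope is opened. From then on the man and the treating staff know the schedule, and every efficacy result is a subjective rating. Two routes of influence remain that the plan could close cheaply.

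- **Staff.** If treating staff talk with the man before or during completion, their view of the schedules can color his answers.
- **Analyst.** The plan leaves choices open. Section 10.1 names IIEF-EF as primary, 10.5 names SEP2 pass rates as co-primary, 3.1 lists three follow-up times with none designated primary, and the success rates in 10.5 are undefined. With the arms visible, these choices can be made knowing which schedule they favor.

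A third exposure concerns baseline. If the man already knows his arm when he answers the baseline forms, change from baseline can differ between arms because of the starting score.

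At stake is whether a reported difference between A and B reflects the schedules.

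**Working it through.** **1. The plan's own figure.** Section 10.5 gives power 0.852 for 5% against 35%, alpha 0.025, 40 per group. The Walters approximation is Φ(√(2n)·[arcsin√(p2 − 1/(2n)) − arcsin√(p1 + 1/(2n))] − z). With n = 40 and two-sided alpha 0.025:

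- √80 × (arcsin√0.3375 − arcsin√0.0625) = 8.944 × (0.620 − 0.253) = 3.28
- 3.28 − 2.24 = 1.04, and Φ(1.04) = 0.85

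Unrounded, the result is 0.852. Full enumeration of Fisher's test gives 0.850. The figure reproduces and is not disputed here. It concerns each arm against an assumed placebo rate, so it says nothing about A versus B.

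**2. What is and is not protected.**

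| Step | Stated protection | Gap |
|---|---|---|
| Assignment | Sealed envelopes (10.6) | None on this point |
| Baseline forms | The patient answers (7.3) | Whether the arm is already known |
| Follow-up forms | Same self-report forms (Appendices I to IV) | Mode, privacy and order of steps (7.5) |
| Analysis | None (10.5) | Analyst sees the arms |

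**3. Baseline order.** Section 7.3 describes recruitment and randomization first, then the washout instruction, then the baseline forms. Section 10.6 opens the envelope after consent, once the man is about to be treated. Under the 7.3 order he may know his schedule for weeks before answering. Under 10.6 the forms could come just before or just after opening. The text does not settle which.

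**4. Open analysis choices.** Two candidate primary endpoints (IIEF-EF, SEP2) at three follow-up times give 2 × 3 = 6 possible headline results, before counting the repeated-measures comparison of trends.

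**5. Hypothetical size.** Inputs:

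- 40 per arm (10.6).
- SD of change 5.8, an assumption. The number is borrowed from the pilot in 1.4, where it reads as the SD of a score, not of a change.
- A spurious A−B shift d, also an assumption.
- One time point, as a simple stand-in for the planned repeated-measures ANOVA.

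SE = 5.8 × √(2/40) = 1.30. The false-positive rate is Φ(−1.96 + d/SE) + Φ(−1.96 − d/SE).

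| d (points) | d/SE | False-positive rate |
|---|---|---|
| 0 | 0 | 5.0% |
| 0.5 | 0.39 | 6.7% |
| 1.0 | 0.77 | 12.0% |
| 1.5 | 1.16 | 21.2% |

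With an SD of 7.0, the rates for 0.5 and 1.5 points are 6.2% and 16.0%. A noncentral-t calculation at SD 5.8 and 1 point gives 11.9%. For SEP2 with a true rate of 35% in both arms, Fisher's test at two-sided 0.05 rejects 2.8% of the time with no shift and 10.5% with a 10-percentage-point reporting shift in one arm.

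**The case against.** The case against is strong, and most of it stands.

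- **Self-completion is largely there.** The appendices address the man directly, and 7.2 and 7.3 have him answer the forms. It would be wrong to infer that the plan has no protection. Privacy, order of steps and a masked analyst are what is missing.
- **The treating team is an inference.** Men come from the Department of Urology clinic (4.1), are treated in the physician's office (7.4) and are seen at the clinic (7.5). No separate team is named, but who collects the forms is not stated either.
- **Expectation need not differ.** A reader might infer from the cited sham-controlled trial ("mean SEM 6.7 0.9 vs 3.0 1.4") that expectation will create a schedule difference. It does not show that. A 3.0-point sham gain shows the score can move without active treatment. It does not show a difference between two active schedules with equal totals per region (5 × 720 = 6 × 600 = 3,600). The gain may include regression to the mean and is imprecise: read as mean and SEM, 3.0 ± 1.96 × 1.4 runs from 0.3 to 5.7. Section 10.5 does call the arms low and high intensity, but nothing shows that this label reaches the men.
- **Missing statements.** An open-label declaration or neutral wording for participants may sit on the title or consent pages, which were not available. Their absence cannot be held against the plan.
- **Analyst freedom is cured mainly by prespecification.** True. Coding the arms is a second safeguard, not a substitute.

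What survives is that neither the order of steps for the forms nor a coded analysis file is stated, and both cost little.

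**Conclusion.** The point holds as a cheap improvement of low priority. It is not an error in a figure and gives no reason to change the sample size. No supplied section states a protection after allocation, and the order of randomization and baseline assessment is unclear between 7.3 and 10.6. The exposure is residual staff influence, arm-aware analysis choices, and possibly baseline answers given with the arm known.

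Its size is unknown. The documents give neither direction nor magnitude for any difference in influence between arms. The 6.7% to 21% range rests on an assumed shift, an assumed SD of change and a single-time comparison, and is purely hypothetical. A reader might take it as the error that the fix would prevent. It is not: each man still knows his schedule, and any bias from his own expectation would largely survive.

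**What to change.** - **7.3 and 7.5:** each man completes the questionnaires due at that visit himself, in private, before any contact with treating staff.
- **7.3 and 10.6:** reconcile the order of steps so that the baseline forms are completed before the envelope is opened.
- **10.5:** the analyst works on a file with neutral arm codes until the primary analysis is final. Name one primary endpoint and one primary time point at the same time, since masking does not replace that.
- **Limitations:** state that the men know their schedule and that their own expectation cannot be removed.

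The cost is protocol wording, a changed order of steps at visits, a completeness check by existing staff not treating that man, and one person to hold the codes. If envelopes are now opened before the washout, session booking would have to wait until the baseline forms are in. Treatment and sample size are unaffected.
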